8.2 Exclusion Criteria

There are no criteria by which a subject would be excluded.

9 INVESTIGATIVE SITE INFORMATION

9.1 Investigative Site Selection

Sites will be selected for participation based on the following criteria:

- Previous participation in the **remedē** System Pivotal Trial with currently active subjects
- Sufficient resources within site to conduct follow-up requirements of all subjects
- Willingness and interest in conducting the study

At each of the participating sites, it is expected that there will be coordination among the cardiac physician, interventional cardiologist / electrophysiologist, and the sleep medicine physician. The Principal Investigator (PI) is responsible for the overall conduct of the study. The PI may train and designate person(s) to conduct study-related activities but must retain overall responsibility for the trial. All training and delegation of tasks will be documented.

9.2 Ethical Considerations

The study will be conducted according to the Declaration of Helsinki, Protection of Human Subjects (21 Code of Federal Regulations [CFR] 50), IRBs (21 CFR 56), Financial Disclosure by Clinical Investigators (21 CFR Part 54), Electronic Records and Electronic Signatures (21 CFR Part 11), Obligations of Clinical Investigators (21 CFR 312), The International Standard for Standardization (ISO) 14155:2011, and in accordance with local laws and regulations in each of the countries participating.

9.3 Activation Requirements

This protocol and any amendments will be submitted to the FDA, appropriate regulatory bodies and IRB/IEC for approval to conduct the study prior to initiation.

The study will not commence at a participating institution until all investigational site activation requirements are completed. These include:

- Clinical Trial Agreement (signed)
- IRB/IEC approval letter (and national regulatory approval if required)
- Respicardia, Inc. and IRB/IEC-approved informed consent form (ICF) (and national regulatory approval if required)
- Completed Delegation of Authority Form/Delegation of Responsibilities Form
- Training Documentation Form(s) completed for PI, study coordinator, and any other study site personnel completing trial-related activities at the time of activation.
- PI Curriculum Vitae (CV) and sub-investigators' CVs participating at the time of activation
- Clinical Investigational Plan (CIP) signed by the PI
- IRB/IEC membership list/roster or Assurance Document

- Financial disclosure from the PI and sub-investigators participating at the time of activation

9.4 Informed Consent

Consent forms will be submitted with the protocol for review and approval by the IRB/IEC by the study site.

All subjects for this study will be provided an IRB/IEC-approved consent form describing this study and will be provided sufficient information to make an informed decision about their participation in this study.

The formal consent of a subject, will be obtained before that subject is submitted to any study procedure that is not standard of care. Consent forms must be signed by the subject or legal representative, and the investigator-designated research professional obtaining the consent. Respicardia, Inc. and the IRB/IEC must approve alternative informed consent materials prior to use. Where applicable, a local language informed consent will be provided.

9.5 Study Training

Protocol-specific training and education customized to the specific roles of all investigational site personnel will take place prior to site personnel participating in the study and throughout the study as needed. In particular, all physicians delegated to implant the **remedē** System will be trained on standardized procedures for system implantation prior to being authorized to perform **remedē** System modifications or have training documents on file from the **remedē** System Pivotal Trial. All training will be documented and filed in the regulatory binder at the respective investigational site as well as at Respicardia, Inc. All study personnel, including new study personnel added during the course of the study, must be trained and delegated prior to performing any study-related activities considered non-standard of care.

9.6 Study Suspension or Termination

A study suspension is a temporary postponement of some or all of the study activities whereas termination of the study indicates study closure. Study suspension or termination of the study may occur at a single investigational site or for the study as a whole. Possible reasons for considering suspension or early termination include, but are not limited to, the following:

- **Study Suspension or Early Termination**
 - Adverse events associated with the **remedē** System may endanger the safety or welfare of the study subjects
 - Observed and / or suspected performance of the **remedē** System that is different from the product's design intent or specifications in a manner deemed unacceptable

- **Early Individual Investigational Site Termination or Suspension:**
 - Investigational site's noncompliance to the CIP or failure to comply with the country or local regulations
 - Failure to submit data in a timely manner
 - Failure to follow-up on monitoring findings
 - IRB/IEC approval expiration or withdrawal
 - Lack of PI oversight
 - All subjects at the site have completed participation in the trial
 - Fraud or fraudulent misconduct is discovered (as defined by local laws and regulations)

If a study suspension occurs, study subjects who are enrolled and implanted will continue to be followed for safety evaluation and/or per regulatory requirements.

10 STUDY PROCEDURES

Scheduled assessments at each visit are listed below and in **Table 1**. Subjects will start follow-up at the appropriate follow-up visit based on their initial **remedē** System implant date. Subjects are required to complete the informed consent process prior to participation in the study.

Table 1 Follow-up Schedule

		Months ¹ Post Implant								
Assessment	Prior to first visit	30 (phone) ±60 days	36 (office) ±60 days	42 (phone) ±60 days	48 (office) ±60 days	54 (phone) ±60 days	60 (Office) ±60 days	Interim Device Management	System Modification	Study Exit
Follow-up window (days)										
Informed Consent	X									
remedē System assessment			X		X		X	O		
Subject status		X	X	X	X	X	X			X
Adverse event review and reporting		X	X	X	X	X	X	X	X	X
Medical stability ²			X		X		X			
In-home PG			X		X			O		
In-lab PSG							X	O		
ESS				X		X		X		
Concomitant device interaction testing, if applicable								O ³	X	

X=Required at visit, O=Collected/Performed as needed

¹ A month is defined as 30 days for visit target date determinations

² Perform medical stability assessment prior to PG/PSG

³ Concomitant device interaction testing should be repeated prior to therapy initiation and anytime the remedē System or the cardiac device system is modified if applicable

10.1 30, 42, and 54 Month Follow-up

The following assessments will be performed via telephone call:

- Survival
- Adverse event review and reporting
 - Review events with subject and review medical records since last visit

10.2 36 and 48 Month Follow-up

The following assessments will be performed at a clinic office visit:

- Date of visit
- **remedē** System assessment including
 - stimulation lead impedance and capture levels on final programmed electrode pair
 - unipolar stimulation lead impedance measurements
 - interrogation including pre and post device settings parameter printouts
- Medical stability assessment prior to PG (defined as no hospitalizations in the previous 2 weeks)
 - The PG should not be performed until the subject is medically stable for at least 2 weeks
- In-home PG
 - PG is set up in the office and subject is instructed on proper use
 - Must include a minimum of four hours of high quality recording time
- ESS
- Adverse event review and reporting
 - Review events with subject and review medical records since last visit

10.3 60 Month Follow-up

The following assessments will be performed at a clinic office visit:

- Date of visit
- **remedē** System assessment including
 - stimulation lead impedance and capture levels on final programmed electrode pair
 - unipolar stimulation lead impedance measurements
 - interrogation including pre and post device settings parameter printouts
- Medical stability assessment prior to PSG (defined as no hospitalizations in the previous 2 weeks)
 - The PSG should not be performed until the subject is medically stable for at least 2 weeks

- PSG in sleep laboratory
 - Must include a minimum of four hours of high quality recording time including a minimum of 2 hours of sleep
- ESS
- Adverse event review and reporting
 - Review events with subject and review medical records since last visit
- Exit the subject from the trial following completion of the visit

10.4 Interim Device Management

The investigator may evaluate the **remedē** System at any point during the study via office visit, in-home PG, or in-lab PSG. The **remedē** System Implant and Clinician Use Manual should be used by the Investigator or designee to guide the programming options and **remedē** System set up. Respicardia, Inc. personnel may also be available for technical and programming support.

The following assessments should be performed and recorded at an interim device management visit:

- Adverse Event review and reporting
 - Review events with subject and review medical records since last visit
- **remedē** System assessment (optional)
 - stimulation lead impedance and capture levels on final programmed electrode pair
 - interrogation including pre and post device settings parameter printouts

If applicable, concomitant device interaction testing should be repeated prior to therapy initiation and anytime the **remedē** System or the cardiac device system is modified as described in the **remedē** System Implant and Clinician Use Manual.

10.5 System Modifications

In the event the **remedē** System requires modification (i.e., lead repositioning or replacement, system explant, or IPG replacement) the following assessments should be performed:

- Adverse Event review and reporting
 - Review events with subject and review medical records since last visit
- Concomitant device interaction testing, if applicable

In addition, system modifications occurring after exit from the pivotal trial and prior to signing ICF in this trial will be collected.

10.6 Study Exit

If the study exit occurs prior to the 60 Month follow-up visit, the following assessments will be performed:

- Adverse event review and reporting
 - Review events with subject and review medical records since last visit

In addition to subject's exit at study closure or completion of protocol requirements, subjects may be exited from the study for the following reasons and their exit documented on a Study Exit Case Report Form (CRF):

- Subject lost to follow-up
- Subject-initiated withdrawal
- Physician-initiated withdrawal
- Subject death

10.6.1 Subject Lost to Follow Up

In the event the ICF is signed and the subject is lost to follow-up, the study site must make a minimum of two attempts (one certified letter and one documented phone call or two certified letters) to contact the subject. Each attempt to contact a lost to follow-up subject and the method used will be documented in the subject's medical record.

10.6.2 Subject-Initiated Withdrawal

A subject may withdraw from the study at any time by notifying their physician. If a subject withdraws participation in the study at any time, there will be no penalty or loss of future medical care.

10.6.3 Physician-Initiated Withdrawal

The PI may withdraw the subject from the study without the subject's consent at any time if medically justified or for other documented reasons.

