7 STUDY OBJECTIVES

1. Evaluate the survival rate

This endpoint is an assessment of survival in subjects with moderate to severe CSA being treated with the **remedē** System. Survival will be compared to historical controls or newly published results at three and five years post implant. No formal statistical hypothesis will be tested.

2. Evaluate long-term three and five-year device-related Serious Adverse Events (SAEs)

This endpoint is an assessment of long-term safety via summary of anticipated or unanticipated device-related SAEs. Events must meet the definition of serious as defined in [Section 10.8](#). Device-related SAEs include device explants due to device-related infection and events such as: device malfunction, lead fracture, lead component failure, lead dislodgment, lead displacement, pocket perforation, or extra-respiratory sensation requiring lead revision. **remedē** System IPG replacement for battery depletion will not be considered a device-related SAE unless it is earlier than anticipated. The number of events and subjects with an

event will be summarized through each time point. No formal statistical hypothesis will be tested.

3. Evaluate long-term three and five-year therapy-related SAEs

This endpoint assesses the safety of the **remedē** System by evaluating anticipated or unanticipated therapy-related SAEs. Therapy-related SAEs must meet the definition of a SAE as defined in [Section 10.8](#) and include events such as diaphragmatic stimulation discomfort, extra-respiratory stimulation, or concomitant device interaction. The number of events and subjects with an event will be summarized through each time point. No formal statistical hypothesis will be tested.

4. Evaluate the AHI, CAI, and obstructive apnea index (OAI) at three years using in-home polygram (PG) and at five years using in-lab polysomnogram (PSG)

This effectiveness endpoint will be assessed by summarizing the AHI, CAI, and OAI at three and five years, as well as change from baseline at five years. No formal statistical hypothesis will be tested.

5. Evaluate the change in quality of life from baseline to three and five years using the ESS

The ESS is a validated instrument that assesses a subject's daytime sleepiness. The objective is to demonstrate a reduction in the ESS score from baseline at three and five years. No formal statistical hypothesis will be tested.

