11 STATISTICAL METHODS

11.1 General Statistical Considerations

Data from this study will be combined with data from the **remedē** System Pivotal Trial. All subjects will be pooled for analysis regardless of original randomization assignment.

Descriptive statistics will be used to summarize data. Continuous variables will be summarized using means, standard deviations, medians, interquartile ranges, minimums and maximums. Categorical variables will be summarized by calculating the percent of subjects in each category. No imputation for missing data will be performed.

Statistical analyses will be performed using validated software (e.g., SAS).

Copies of databases used to prepare clinical report summaries will be archived to enable any statistical analyses performed to be replicated.

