11.3 Data Analyses

All subjects randomized in the **remedē** System Pivotal Trial will be included in the safety assessments, unless otherwise noted. All adverse events will be summarized by seriousness, relatedness, and temporal relationship to the procedure and will be analyzed in a descriptive fashion. The number of events and number of subjects experiencing events will be summarized.

The survival distribution will be estimated with a Kaplan-Meier curve and the 95% confidence interval for the three and five year (or other time point of interest) survival rates will be calculated using the standard error determined by the Peto method.¹ The survival rate will be compared to historical controls and/or newly published results.

Subjects with follow-up data at the visit of interest will be included in the effectiveness assessments. Change from baseline analyses will include subjects with baseline and follow-up visit data.

Additional exploratory and/or subgroup analyses may also be performed to characterize study outcomes.

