 - Subject completed study follow-up requirements
 - Subject Lost to Follow-up
 - Subject-Initiated Withdrawal
 - Physician-Initiated Withdrawal
 - Subject Death
 - Early termination of site or study
- If lost to follow-up, subject or physician initiated withdrawal or early termination: Date of last contact

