1.9.4.1.4 Trial Withdrawals

A total of 43 subjects had exited the trial as of the datalock. Table 6 displays the reasons for trial discontinuation.

Table 6 Summary of Reasons for Trial Withdrawals

	Treatment (N=73)	Control (N=78)	Pooled (N=151)
Exit reason	% (n) Subjects	% (n) Subjects	% (n) Subjects
Physician-initiated withdrawal	1% (1)	3% (2)	2% (3)
Subject Death	15% (11)	14% (11)	15% (22)
Subject Lost to Follow-Up	1% (1)	1% (1)	1% (2)
Subject-initiated withdrawal	8% (6)	5% (4)	7% (10)
System explanted ¹	7% (5)	1% (1)	4% (6)
Total	33% (24)	24% (19)	28% (43)

¹2 subject-initiated withdrawals also underwent system explant

Subjects exited for the following reasons:

- Physician-initiated withdrawals for three (3) subjects
 - Two (2) due to intervening medical conditions
 - One (1) exit from the trial subsequent to a failed implant attempt

- Subject death for 22 subjects
- Lost to follow-up for two (2) subjects
 - One (1) subject after an unsuccessful implant attempt
 - One (1) subject became unreachable despite multiple attempts by the investigational site to contact the subject

Note: Neither subject had therapy initiated at the time of being lost to follow-up

- Subject-initiated withdrawals for ten (10) subjects
 - Four (5) subjects withdrew due to intervening medical issues
 - Three (3) subjects withdrew due to relocating away from study site
 - Two (2) withdrew consent subsequent to failed implant attempts
- Withdrawal due to explanted **remedē®** Systems occurred in six (6) subjects. Two (2) subject-initiated withdrawals also had the system explanted as outlined in Section 1.9.4.1.3

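### No vital status is obtained after a subject leaves the study, so three- and five-year survival is at risk of modest upward bias if subjects who leave ill die sooner

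*Combined protocol and SAP*

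**What the plan says.** **Endpoint.** Survival is the first objective in Section 7: "Survival will be compared to historical controls or newly published results at three and five years post implant". No hypothesis is tested. Section 11.3 states that "The survival distribution will be estimated with a Kaplan-Meier curve", with confidence intervals from the Peto standard error. Section 11.1 adds "No imputation for missing data will be performed". Neither section gives a censoring rule.

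**Leaving the study.**
- Section 10.6.3: "The PI may withdraw the subject from the study without the subject's consent at any time if medically justified or for other documented reasons".
- Section 10.6.2: the subject may withdraw at any time.
- Section 10.6.1: at least two attempts must be made to reach a lost subject, by certified letter or by letter and phone. No check of death records or next of kin is required.

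**At exit.** Section 10.6 reads "If the study exit occurs prior to the 60 Month follow-up visit, the following assessments will be performed" and lists an adverse event review that includes medical records. Table 1 also marks "Subject status" as required at Study Exit.

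**After exit.** Section 10.8 collects adverse events up to study exit. Besides exit date and reason, the Study Exit form in Appendix C asks for one further item: "If lost to follow-up, subject or physician initiated withdrawal or early termination: Date of last contact". No later contact or record search is scheduled.

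**The concern.** The study observes subjects who already have the implant. Three of its six scheduled contacts (30, 42 and 54 months) are phone calls for survival and adverse events. A subject who can no longer manage a sleep study or an office visit could still be followed for survival at almost no burden. The withdrawal sections do not make that distinction: whoever leaves, for whatever reason, leaves survival follow-up too.

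Kaplan-Meier assumes that a censored subject has the same future risk as those still followed. Withdrawal for a medical reason is the kind of exit for which that may fail. The pivotal trial shows that such exits occur. Its summary in Appendix F (Section 1.9.4.1.4) says of the three physician-initiated withdrawals: "Two (2) due to intervening medical conditions". Half of the ten subject-initiated withdrawals were also for medical issues. There is no concurrent arm in which a similar loss could offset the effect, so any error passes straight into the comparison with historical results.

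**Working it through.** **1. Reproduce the pivotal exits (Appendix F, Table 6).** 3 physician-initiated + 22 deaths + 2 lost + 10 subject-initiated + 6 explanted = 43. 43/151 = 28.5%, printed as 28%. The table reproduces.

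**2. Keep only exits that can recur here.** Non-death exits: 43 − 22 = 21.
- Four followed failed implant attempts (1 physician-initiated, 1 lost, 2 subject-initiated). They cannot recur, because only implanted subjects are eligible.
- Six were recorded as system explanted. Here an explant is a system modification (Section 10.5), not an exit reason (Section 10.6).

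21 − 4 − 6 = 11. Check: 2 physician-initiated + 8 subject-initiated + 1 lost = 11.

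**3. Exits for medical reasons.** 2 physician-initiated + 5 subject-initiated = 7. The manual prints both four and five for the second figure; only five fits the stated total (5 + 3 + 2 = 10).

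**4. Scale to this study.** Assumption: pivotal fractions apply to the maximum of 94 enrolled.
- Non-death exits: 11/151 × 94 = 6.8, about 7.
- For medical reasons: 7/151 × 94 = 4.4, about 4.

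**5. Overstatement of survival.** Censoring already credits these subjects with average mortality, so only excess deaths count:

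overstatement = (d − m × p) / 94

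Here m = 4.4 censored subjects, d is the number who die by month 60, and p is the mortality that censoring implies. The documents do not give p; 10 to 30% is assumed.

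| Deaths d | p = 10% | p = 30% |
|---|---|---|
| equal to m × p | 0 | 0 |
| 2 | (2 − 0.44)/94 = 1.7 points | (2 − 1.32)/94 = 0.7 points |
| 4 (nearly all) | (4 − 0.44)/94 = 3.8 points | (4 − 1.32)/94 = 2.9 points |

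These are points of survival from entry into this study. On the curve from implant they are multiplied by survival up to entry, so they are somewhat smaller.

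**6. Compare with the precision.** Peto half-width = 1.96 × S × √((1 − S)/n), with S and n assumed.
- S = 0.80, n = 94: 7.2 points.
- S = 0.70, n = 50: 10.6 points.

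**7. Cross-checks.**
- At the pivotal datalock, actuarial survival with the 7 medical exits censored is 1 − 22/(151 − 3.5) = 85.1%. If all 7 had died it is 1 − 29/151 = 80.8%. The ceiling is 4.3 points, the same order as step 5.
- A constant-hazard model over the full five years from implant lets medical withdrawals continue at the pivotal rate. It assumes 1.5 to 2.5 years to datalock and post-exit hazard ratios of 2 to 8. It gives 1.2 to 7.2 points at five years, and 0 at a hazard ratio of 1. It includes withdrawals during the pivotal trial, which a change to Section 10.6 cannot reach, so it is an outer bound and not the size of this point.

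**The case against.** **Withdrawal is a permission, not a route for the sick.** Nothing in the plan makes a subject leave because a visit or sleep study is missed. Sleep studies wait until the subject is medically stable (Sections 10.2 and 10.3). The visit form accepts a visit that was not completed, and the deviation form lists visits and assessments not done (Appendix C). A reader might infer that subjects too ill for procedures must be withdrawn; the documents do not say so. This stands. What remains is that the plan does not ask sites to keep such subjects in follow-up.

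**Status is checked at exit.** A reader might infer that no vital-status check exists at all. Table 1 and Section 10.6 show otherwise. The gap concerns deaths after exit. Section 10.6.4 asks sites to retrieve information on deaths away from the site, but that helps only once a death is known. Two contact attempts is a minimum, so a site may do more.

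**The consent form was not in the reviewed text.** It may address contact or data use after withdrawal, so whether it needs a new line is open.

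**Illness is not the same as approaching death.** One elective explant in Appendix F (Section 1.9.4.1.3) concerned a subject who left because of depression. The documents report no mortality after exit.

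**The consequence is limited.** Survival is descriptive, with no success criterion, and physician-initiated withdrawal was rare (3/151 = 2.0%). Both are true. They lower the priority but do not close the gap.

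**Conclusion.** The plan as written can miss deaths among subjects who leave, and it does not say how those subjects are censored. Censoring at last contact is the natural reading, but it is an inference. Survival is therefore at risk of upward bias. A reader might go further and conclude that it is biased upward. The documents do not support that: the bias is zero if leavers die at the same rate as those who stay, and nothing reports how they fare.

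A reader might also scale all 21 pivotal non-death exits to this study and count each unseen death in full. That overstates the size, because ten of those exits were failed implants or explants and because censoring already implies some deaths.

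On the narrower count the effect is about 0.7 to 1.7 points, and below 4 points in the near-worst case. This rests on three assumptions: pivotal exit fractions over the remaining follow-up, 94 subjects enrolled, and 10 to 30% implied mortality. It lies inside the likely half-width of 7 to 11 points. However, the interval does not allow for informative censoring, and if sicker subjects leave, the error always favours the device. The point justifies an inexpensive change and does not invalidate the survival analysis.

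**What to change.** - **Sections 10.6.2 and 10.6.3:** separate stopping study procedures or visits from ending vital-status follow-up. A physician-initiated withdrawal stops procedures only; the subject stays in the existing survival contacts unless the subject declines. At a subject-initiated exit, ask for permission for vital status only and record the answer.
- **Section 10.6.1:** before loss to follow-up is entered, require a check of medical records, next of kin or public death records, where consent and law allow. Repeat it at 36 and 60 months post implant.
- **Section 11.3:** state that censoring is at the last date known alive. Add one sensitivity analysis for subjects censored before 60 months, for example with higher assumed mortality after exit.
- **Appendix C, Study Exit form:** add a field for permission for vital status and the last date known alive.

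The cost is protocol wording, a form change, possibly a line in the consent form, and a short record check for a handful of subjects (about 7 on the assumption above). The survival figure may become slightly less favourable. No treatment or study procedure changes.
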